- 1. Primary outcome: The group treated with MSA adjunctive to ADT will show a greater mean change from baseline to endpoint in total score as compared to the group treated with placebo (PBO) adjunctive to ADT as measured by the
 - a. Massachusetts General Hospital Cognitive-Physical Function Questionnaire (MGH-CPFQ)
- 2. Secondary outcome:
 - a. MSA adjunctive to ADT will demonstrate clinically acceptable safety and tolerability, compared to placebo, based on
 - i. spontaneously reported adverse events and significant adverse events
 - ii. significant changes in blood pressure and pulse
 - iii. significant changes in weight
 - iv. significant changes in electrocardiogram
 - v. significant changes in the Rush Sexual Inventory
 - b. The group treated with MSA adjunctive to ADT will show a greater mean change from baseline to endpoint as compared to the group treated with PBO adjunctive to ADT as measured by the change on
 - i. MGH-CPFQ individual item analysis
 - ii. MADRS scores:
 - 1. Total score
 - 2. Subscales
 - 3. Individual item analysis
 - 4. Percent of "responders" (\geq 50% reduction in score baseline to endpoint)
 - 5. Percent reaching "remission" (score of ≤ 10 at endpoint)

- c. The group treated with MSA adjunctive to ADT will show statistically significant improvement in core residual symptoms of MDD extant on monotherapy ADT as measured by the
 - i. PGI (Patient Impression and Improvement) scales
 - ii. Quick Inventory of Depressive Symptomatology-16 (QIDS-16) total score (≤ 6) and subscale
 - iii. Clinical Global Impression-Severity (CGI-S); and, Clinical Global Impression-Improvement (CGI-I)
 - iv. QIDS total score and subscale
- d. The group treated with MSA adjunctive to ADT will show statistically significantly improvement in overall functioning (work, social and cognitive) when compared to the group treated with PBO and ADT as measured by the
 - i. Total and individual item scores from the HDRS-17 and -28
 - ii. Maier and other subscale scores from the HDRS-17 and -28
 - iii. Scale For Assessment Of Negative Symptoms (SANS)
 - iv. Health Status Questionnaire, 2nd ed. (HSQ 2.0)
 - v. SF-36 Health Survey (SF36)
 - vi. Fawcett Experienced Pleasure Index (EPI)
 - vii. Endicott Work Productivity Scale (EWPS)
 - viii. Sheehan Disability Scale (SDS)
 - ix. Fatigue Associated with Symptoms of Depression (FASD)

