- **Study Design:** A randomized, double-blind, placebo-controlled, parallel-group study of flexible dose mixed salts amphetamine (5-60 mg) adjunctive to antidepressant therapy among adult outpatients with major depressive disorder responding inadequately to current antidepressant therapy.

Fig. 1: Treatment Groups

Visit	Phase	Weeks	Group	Group	Procedures
		on med	1	2	
V1		Scr			Inclusion/Exclusion
V2		0			Baseline measurement + disp.
V3	Ι	1	MSA	PBO	Measure effect of 1 week on study med + disp.
V4	Ι	2	MSA	PBO	Measure effect of 2 weeks on study med + disp.
V5	Ι	3	MSA	PBO	Measure effect of 3 weeks on study med + disp.
V6	II	4	MSA	MSA	Measure effect of 3 weeks on study med + disp.
V7	II	5	MSA	MSA	Measure effect of 3 weeks on study med + disp.
V8	II	6	MSA	MSA	Measure effect of 3 weeks on study med
V9		(8)			Safety follow-up

Fig. 2: Study Design Overview

The treatment phase of the study consists of 2 phases (21 treatment days per phase). Study Phase 1 will consist of visits 2 (baseline) through 5. Study Phase 2 will consist of visits 6 through 8. There will be a follow-up visit 2 weeks following visit 8. There is a one-week interval between study visits, with a scheduling window of \pm 3 days allowed.

Mixed salts amphetamine is FDA-approved for Attention Deficit-Hyperactivity Disorder (ADHD) and superior in efficacy to placebo; therefore, comorbid ADHD will be statistically controlled as a continuously-variable covariate, but will not be considered an exclusionary condition.

The primary analysis will be a repeated measures analysis of variance using a mixed-effects model (PROC MIXED-MMRM). The primary outcome measure will be the MGH-CPFQ total score at baseline and the MGH-CPFQ total score at the end of the trial. The independent variables will be the study visit, the treatment in the previous phase, and treatment assignment. The variance covariance matrix for the repeated measures will be unspecified.

Enrollment Period: The enrollment period is estimated to be 6 months. The last patient is expected to complete the study by March 31, 2010.

Number of Subjects: 40 subjects will be randomized (20 to each treatment arm). Additional subjects may be consented to allow for screen failures. Subjects who terminate early post-randomization will be replaced only sufficiently to ensure a total number of 24 (12 to each treatment arm) evaluable subjects.

Duration of Subjects' Study Participation: There will be a total of 9 study visits over a period of 9 weeks.

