Study Assessments and Primary Endpoints: The difference in absolute change in score from baseline to endpoint in the MGH-CPFQ between the MSA and the PBO groups is the primary endpoint. Key secondary endpoints will be difference in absolute change from baseline in MADRS score between MSA and PBO, difference in remission rates (MADRS < 11) between MSA and PBO, the change from baseline in total score at endpoint of MGH-CPFQ item analysis, difference in change scores on the CGI-S, CGI-I and QIDS. Safety outcome measures: adverse events, physical examinations, vital signs; blood pressure, orthostatic; EKG; Rush Sexual Inventory (RSI).

Statistical Methods: The randomized sample includes all patients who are randomized. The Safety sample will include those randomized patients who received at least one dose of doubleblind study medication as indicated on the dosing record. The efficacy sample will include those patients in the safety sample who have at least one efficacy evaluation post-randomization. The last observation carried forward (LOCF) data set includes data recorded at a given visit after randomization, or, if no observation is recorded at that visit, data carried forward from the previous postrandomization visit. The LOCF data set is primary, and analysis of the observed case data set also will be conducted.

The primary analysis will compare pooled MGH-CPFQ response rates between PBO and MSA and PBO non-responders. Differences in response rates will be compared using the CMH General Association Test. Descriptive statistics on non-primary groups will be conducted.

This study seeks to estimate the strength of any statistically significant relationship, or effect size, in addition to statistical significance of found treatment effects.

Secondary Endpoints Analysis: Differences in remission (defined as an endpoint MADRS score <11) rates will be compared using the CMH General Association Test. Logistic regression analysis will be performed to explore the relationship between response and patients' demographics and prognostic variables including baseline QIDS score, gender, site, and age, etc. Similar analyses will be performed for remission.

Fig. 3	: Stud	y Proce	dures	Table
--------	--------	---------	-------	-------

			Treatment period 1			Treatment period 2			
Study Visit	V1 Screen	V2 Baseline	V3	V4	V5	V6	V7	V8	V9 F/UP
End of Week	-1	0	1	2	3	4	5	6	8
Day	-7	0	7	14	21	28	35	42	56
Informed consent	Х								
Demographic data	Х								

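### Hypotheses 2c and 2d predict statistically significant benefit over many scales, items and open-ended subscales, with no alpha, order, adjustment or success rule

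*Combined protocol and SAP*

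**What the plan says.** Under Research Hypotheses, item 2d predicts that MSA added to ADT "will show statistically significantly improvement in overall functioning (work, social and cognitive) when compared to the group treated with PBO and ADT". The claim is attached to nine entries. Seven are separate scales: SANS, HSQ 2.0, SF-36, EPI, EWPS, SDS and FASD. The other two are "Total and individual item scores from the HDRS-17 and -28" and "Maier and other subscale scores from the HDRS-17 and -28", and the second has no closed list.

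Item 2c makes a parallel prediction, that the MSA group "will show statistically significant improvement in core residual symptoms of MDD extant on monotherapy ADT", measured by the PGI scales, QIDS-16 total and subscale, CGI-S and CGI-I. Item 2b predicts only a greater mean change and does not mention significance.

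Under Statistical Analysis, the key secondaries are introduced with "Key secondary endpoints will be difference in absolute change from baseline in MADRS score between MSA and PBO". The list goes on to MADRS remission, CPFQ items, CGI-S, CGI-I and QIDS. They are worded as differences, and none of the 2d scales is among them. Statistical Methods adds a general aim: "This study seeks to estimate the strength of any statistically significant relationship, or effect size, in addition to statistical significance of found treatment effects".

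The only hierarchy is the set of labels primary, secondary and key secondary. No significance level, sidedness, order of testing, gatekeeping or adjustment is given, and nothing says whether one, some or all 2d measures must succeed.

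**The concern.** A claim of statistical significance implies a known error rate. Here one conclusion, better overall functioning, can be reached through many measures, and the plan does not say what result would establish it. If one nominally significant scale is enough, the error rate of the claim is that of the best result among many. Because one entry is open-ended, the number of tests cannot even be counted in advance.

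The trial randomizes 40 subjects, 20 per arm, and guarantees only 24 evaluable (12 per arm). In a sample of that size an isolated small p-value on one scale is weak evidence, yet the present wording would let it be reported as significantly improved functioning.

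**Working it through.** The plan gives no error rate to reproduce, so the calculation rests on stated assumptions.

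**Which 2d entries can be tested against placebo.** Fig. 1 and Study Procedures put Group 2 on placebo in Phase 1 and on MSA in Phase 2. V5 closes Phase 1, and Phase 2 drug is dispensed there. Fig. 3 then shows:

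- SANS, HSQ 2.0, SF-36, EPI, EWPS, SDS and FASD are collected at every visit from V1 to V8, so all seven have a V5 value under concurrent placebo.
- HDRS-17 and HDRS-28 are collected at V1, V2 and V8 only. At V8 both groups are assigned MSA, so no HDRS total, item or subscale has a concurrent placebo comparison after baseline.
- CGI-S and PGI-S are collected at V1 and V2 only, so neither has a post-baseline value on the schedule.

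This leaves k = 7 tests for 2d, counting one test per scale.

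**Assumptions not in the documents.** Each test is at two-sided 0.05, which is 0.025 in the direction favouring MSA. Any one success supports the claim. MSA has no effect on any of the seven scales. The correlation ρ between test statistics is unknown, so a range is shown.

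**Independent tests.**

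- Either direction: 1 − 0.95^7 = 0.302
- Favouring MSA: 1 − 0.975^7 = 0.162

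**Correlated tests.** The statistics were simulated as Z_j = √ρ·g + √(1−ρ)·e_j, with g and e_j independent standard normal (200,000 draws), counting draws in which the largest value passed 1.96.

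| ρ | At least one false benefit for MSA | At least one false positive, either direction |
|---|---|---|
| 0 | 16.2% | 30.2% |
| 0.3 | 13.6% | 27.0% |
| 0.5 | 11.6% | 22.9% |
| 0.7 | 9.0% | 17.8% |
| 0.9 | 5.7% | 11.5% |
| one test | 2.5% | 5.0% |

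Over ρ from 0 to 0.7 the false-benefit chance is 3.6 to 6.5 times that of a single test (9.0/2.5 and 16.2/2.5).

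**Cost of splitting alpha.** Bonferroni over seven tests gives 0.05/7 = 0.0071 each. Take an assumed standardized effect of 0.8 and the normal approximation Φ(0.8·√(n/2) − z), with n per arm and z the two-sided critical value:

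- 20 per arm: Φ(2.530 − 1.960) = 72% at 0.05, and Φ(2.530 − 2.690) = 44% at 0.0071.
- 12 per arm: Φ(1.960 − 1.960) = 50% at 0.05, and Φ(1.960 − 2.690) = 23% at 0.0071.

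A fixed sequence avoids this loss for the outcomes placed early in it.

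**The case against.** The strongest reply is that this is a small trial meant to generate data and estimate effect sizes, with one named primary outcome. Unadjusted secondary tests do not alter the primary result and could be labelled exploratory at reporting. The first part is correct, and it is why the point is limited to secondary claims. But 2c and 2d do not describe themselves as exploratory. They predict significance, and the label is worth more if fixed before the data are seen.

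A second reply is that if every 2d measure had to succeed, there would be no inflation. That is also correct, but the plan does not adopt that rule, and its silence is the gap.

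Three stronger readings are tempting, and the documents do not support them:

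- *A false functional claim is likely by chance alone.* For the seven testable scales the chance of a false benefit is at most about 16%, and 30% counting both directions. A result favouring placebo could not support improved functioning in any case.
- *The family has dozens of tests.* Ten scale-level tests (seven scales, two HDRS totals, Maier) plus 28 HDRS items make 38. This assumes the 17 items are nested in the 28. The either-direction chance would then be 56% (ρ = 0.5) to 86% (independent). However, the schedule provides no HDRS comparison against concurrent placebo, so these are not valid tests of 2d.
- *The key secondary list also claims significance.* It does not. It names differences. The claims of significance are in 2c and 2d.

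**Conclusion.** The concern holds for 2c and 2d: both predict significance over several measures without the rules that would give the word its meaning. The 9% to 16% for a false functional benefit, and the 18% to 30% in either direction, depend on 0.05 per test, an any-one-succeeds rule, one test per scale, evaluation at V5, and correlation between 0 and 0.7. Higher correlation would lower the figures; testing further subscales or items would raise them. The primary comparison is not affected. The change is worth making because it is confined to wording and prevents one chance result from being reported as a significant functional benefit.

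**What to change.** 1. State the significance level and sidedness.
2. Name one functional score at V5 as the single test of 2d, for example the SDS total.
3. Put that score and the key secondaries in one fixed sequence. It opens only if the primary CPFQ test succeeds and stops at the first non-significant result. Two separate ungated families at 0.05 would not be enough: if independent, their combined error would be 1 − 0.95² = 9.75%.
4. Admit to the sequence only outcomes with a post-baseline assessment under concurrent placebo. MADRS change, MADRS remission, QIDS change and CGI-I qualify at V5. CGI-S does not, as it is scheduled only at V1 and V2.
5. Label all other 2c and 2d measures, all item analyses and all subscales descriptive, reported with estimates and confidence intervals but without claims of significance.
6. Delete 'and other' from the HDRS subscale entry.

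The gate in step 3 needs one identified primary test. Study Design describes a mixed model on the CPFQ total, while Statistical Methods describes a comparison of CPFQ response rates, so the plan must say which of them opens the sequence.

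The cost is that fewer secondary outcomes can be called significant. Data collection does not change and every estimate is still reported.

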- 11) Pregnant or breastfeeding women.

Study Procedures: Figure 3 shows study procedures to be performed at each visit. No study procedures will be performed until a subject signs the informed consent document.

Screen visit (Visit 1): Medical and psychiatric history will be taken, a physical examination and vital signs will be performed and lab tests done. Lab tests include CBC, CMP, urine drug screen and urine pregnancy test for females of childbearing potential. If a subject has had the required lab tests performed within the past 3 months and can produce the results, lab procedures may be waived at the screening visit for that patient (except urine pregnancy test). The HDRS-17 score upon screening will be used to determine entry eligibility (see inclusion criteria). Beyond the patient's verbal report, we will attempt to obtain medical records (e.g., previous clinician or pharmacy records) to document adequate dose and duration of previous/current ADT.

Study Phase 1

Baseline visit (Visit 2): Screened and eligible subjects will return one week after the screening visit. At this visit (provided entry criteria continue to be met) subjects will be randomized in double-blind fashion to one of two treatment groups:

- Group 1: MSA during both phases; or
- Group 2: PBO during Phase 1 followed by MSA during phase 2

Study drug will be dispensed to the subject in sufficient quantity to last until the next study visit (7 days +/-3).

Study visits 3-5: Following the baseline visit, subjects will return at one-week intervals for study visits 3-5. Study procedures to be performed are reflected in Figure 3. Phase 2 study drug is dispensed at study visit 5.

Study visits 6-8: Subjects will return at one-week intervals for study visits 6-8. Study procedures to be performed are reflected in Figure 3. At visit 8, all subjects will receive instructions for tapering the dose of the MSA to avoid potential difficulties from abrupt discontinuation of the study drug.

Study visit 9: Subjects will return two weeks following visit 8 for a safety follow-up check. Procedures to be performed are reflected in Figure 3.

If a subject withdraws or is terminated early from the study, visit 9 procedures will be performed at the final study visit.

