Medical and psychiatric history	Х	Х							
SCID	х								
Physical exam	Х								
Vital signs and weight	Х	Х	Х	Х	Х	Х	Х	Х	Х
EKG	Х								Х
Lab tests*, urine pregnancy test** and urine drug screen	х								х
MGH-ATRQ	Х								
Inclusion/exclusion criteria	Х	Х							
Randomization		Х							
Expectation ratings		Х							
Clinician-completed surveys:									
HDRS (17- and 28-item)	Х	Х						Х	
MADRS		Х	Х	Х	Х	Х	Х	Х	
CGI-S	х	Х							
CGI-I			Х	Х	Х	Х	Х	Х	
C-SSRS	х	Х	Х	Х	Х	х	Х	Х	х
Patient-completed surveys:									
MGH-CPFQ	Х	Х	Х	Х	Х	Х	Х	Х	
EWPS	х	Х	Х	Х	Х	х	Х	Х	
Fawcett EPI	Х	Х	Х	Х	Х	Х	Х	Х	
FASD	Х	Х	Х	Х	Х	Х	Х	Х	
HSQ 2.0	Х	Х	Х	Х	Х	Х	Х	Х	
PGI-S	х	Х							
PGI-I			Х	Х	Х	Х	Х	Х	
RSI	Х	Х	Х	Х	Х	Х	Х	Х	
QIDS-16	Х	Х	Х	Х	Х	Х	Х	Х	
SANS	Х	Х	Х	Х	Х	Х	Х	Х	
SDS	Х	Х	Х	Х	Х	Х	Х	Х	
SF-36	Х	Х	Х	Х	Х	Х	Х	Х	
Study drug dispensed		Х	Х	Х	Х	Х	Х	Х	
Study drug accountability			Х	Х	Х	Х	Х	Х	Х
Concomitant therapy	Х	Х	Х	Х	Х	Х	Х	Х	Х
Adverse events	Х	Х	Х	Х	Х	Х	Х	Х	Х

*Including CBC and CMP. If patient can produce lab results for CBC and CMP performed within the past 3 months, screening procedures may be waived. **For females of childbearing potential

- Angst J. (1992). How recurrent and predictable is depressive disorder? In: Montgomery S, Rouillon F, eds. *Long-term treatment of depression perspectives in psychiatry*. Chichester, UK: John Wiley & Sons Ltd., Vol. 3, p.13.
- Carvalho AF, Machado JR & Cavalcante JL (2008). Augmentation strategies for treatmentresistant depression. *Current Opinion in Psychiatry*, 22 : 7–12.
- Chiarello RJ & Cole JO (1987). The use of psychostimulants in general psychiatry. *Archives of General Psychiatry*, 44, 286-295.

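### Comorbid ADHD is admitted on the promise of a continuous covariate, but no ADHD severity score is scheduled and neither description of the primary analysis has an ADHD term

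*Combined protocol and SAP*

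**What the plan says.** Study Design gives the reason for an adjustment: "Mixed salts amphetamine is FDA-approved for Attention Deficit-Hyperactivity Disorder (ADHD) and superior in efficacy to placebo". From this it concludes that "comorbid ADHD will be statistically controlled as a continuously-variable covariate", "but will not be considered an exclusionary condition". No exclusion criterion names ADHD.

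The next paragraph of the same section describes the primary mixed model: "The independent variables will be the study visit, the treatment in the previous phase, and treatment assignment". The Statistical Methods paragraph describes a different primary analysis, on response rates: "Differences in response rates will be compared using the CMH General Association Test". The only regression that lists covariates is the logistic model under Secondary Endpoints Analysis, which is exploratory and names "prognostic variables including baseline QIDS score, gender, site, and age, etc".

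Fig. 3 is the list of assessments by visit. The row that could capture ADHD most directly is "Medical and psychiatric history", scheduled at V1 and V2. The text on the screening visit adds only that "Medical and psychiatric history will be taken, a physical examination and vital signs will be performed and lab tests done".

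**The concern.** Adjustment is the safeguard the plan offers for enrolling patients whose comorbid condition the study drug is known to treat. The safeguard needs a score to enter and a model to enter it into, and the plan supplies neither. An analyst who follows it would have to drop the promise or choose a variable after the data exist.

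Two things are at stake. In a trial this small, a chance difference between arms in the number of ADHD patients goes uncorrected, and whatever precision the covariate would have bought is lost. Separately, the primary outcome is a cognitive and physical function scale, so a benefit from treating ADHD could be read as a benefit on residual depressive symptoms.

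**Working it through.** **Consistency check**

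| Needed for the promised adjustment | What the plan contains |
|---|---|
| A continuous ADHD score | Fig. 3 lists the SCID, the MGH-ATRQ and a long set of depression, fatigue, function, pleasure and sexual-function instruments. No ADHD scale appears at any visit, and no text says how, when or by whom ADHD is scored. |
| A place in the mixed model | The listed terms are visit, prior-phase treatment and assigned treatment. |
| A place in the CMH test | No ADHD stratum is named. |
| Balance by design | Blocked randomization, with no stratification by ADHD stated. |

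The eligibility criteria use the SCID for the depression diagnosis and for substance use disorder; no ADHD use is stated.

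**Illustration of size**

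From the plan: 20 randomized per arm, with a floor of 12 evaluable per arm. The plan states no prevalence, alpha, power, SD or effect size, so the rest is assumed: ADHD prevalence p of 10%, 20% or 30%, and a difference of 0.5 to 1 SD in MGH-CPFQ change between patients with and without ADHD.

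*Chance imbalance.* Treat the ADHD counts A and B in the two arms as independent binomial(n, p) and sum P(A = a)·P(B = b) over all pairs with |a − b| ≥ 3:

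| n per arm | p = 10% | p = 20% | p = 30% |
|---|---|---|---|
| 20 | 0.18 | 0.32 | 0.39 |
| 12 | 0.08 | 0.20 | 0.26 |

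These count imbalance in both directions, so about half of it would work against MSA.

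*Shift in the treatment difference.* Shift = imbalance in proportion × ADHD difference in change.
- At 20 per arm, 3/20 = 0.15, so the shift is 0.15 × 0.5 = 0.075 SD to 0.15 × 1 = 0.15 SD. The standard error of the difference is √(2/20) = 0.32 SD, so the larger value is 0.15/0.32 = 0.47 of a standard error.
- At 12 per arm, 3/12 = 0.25, so the shift is 0.125 to 0.25 SD. The standard error is √(2/12) = 0.41 SD, so the larger value is 0.25/0.41 = 0.61 of a standard error. This gap is less likely than at 20 per arm, as the table shows.

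*Precision.* A baseline covariate with correlation r to the outcome multiplies the variance by 1 − r². At an assumed two-sided 0.05 and 80% power, the detectable standardized difference is √(2(1 − r²)/n) × (1.96 + 0.84):

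| n per arm | unadjusted | r = 0.2 | r = 0.3 | r = 0.5 |
|---|---|---|---|---|
| 20 | 0.89 | 0.87 | 0.85 | 0.77 |
| 12 | 1.14 | 1.12 | 1.09 | 0.99 |

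The gain is small unless ADHD severity predicts the outcome fairly strongly.

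**The case against.** The covariate sentence stands directly above the model sentence, and the two can be read together as an ADHD covariate plus the listed terms. On that reading the plan is under-specified and has not abandoned the adjustment. This is a fair reading of the model, and the text does not show that adjustment was deliberately dropped. It does not rescue the promise, because no continuous score is scheduled to enter. The open-ended list in the logistic regression might admit ADHD too, but that analysis is exploratory.

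A reader might infer that the trial will hold no information on ADHD at all. The documents do not support that. Psychiatric history is taken at V1 and V2 and could yield a yes/no diagnosis. What is missing is a dedicated or continuous measure.

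A reader might also infer that the primary comparison is biased. It is not: under randomization the imbalance averages to zero and is already reflected in the test's error rate. The endpoint is change from baseline, so a stable ADHD-related difference in level largely cancels, and a 1 SD difference in change is a strong assumption. These points hold, and they keep the numerical consequence modest.

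Finally, a main-effect covariate would not separate ADHD benefit from benefit on residual depressive symptoms. That question remains even with perfectly balanced arms, so delivering the promise exactly would leave it open.

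**Conclusion.** The point holds as an internal contradiction: the plan makes continuous adjustment its answer to admitting ADHD, schedules no score for it, and names ADHD in neither version of the primary analysis. That conclusion rests on the text alone.

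The statistical cost is uncorrected chance imbalance and some lost precision. Under the assumed prevalence and ADHD effect, a three-patient gap at 20 per arm is plausible and moves the estimate by less than half a standard error. These figures are illustrative, since the documents give neither input. The cost to interpretation, an MSA effect that may partly be treatment of ADHD, cannot be sized from the documents. The repair is cheap and worth making before any data are unblinded.

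**What to change.** In Study Design, replace the continuous covariate with a yes/no baseline ADHD diagnosis, recorded before randomization from the psychiatric history already taken. Name it as a term in the primary model of MGH-CPFQ change or, if the CMH analysis is kept, as its stratification factor. The two descriptions of the primary analysis have to be reconciled first, so that the term has one defined place. A sponsor who prefers a continuous covariate can instead add a brief self-report ADHD scale to Fig. 3 at V1 or V2, before randomization, and enter its score.

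In either case, also report the primary result without ADHD patients, labelled descriptive, because the main-effect term does not answer the question of where the benefit arises.

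The cost is a few sentences and one case report form item, or one short questionnaire. A yes/no flag is cruder than a score and uses one degree of freedom. It may also rest on few patients (10% of 40 is 4), which would leave a CMH stratum very sparse.

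Adjustment for baseline MGH-CPFQ is a separate matter. Study Design counts the baseline score as part of the modelled outcome, so it cannot also be a predictor until the outcome is defined as post-baseline change.

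### The primary MGH-CPFQ outcome is read at the end of the trial (Visit 8), when both groups are on MSA; no section names the Visit 5 contrast that would test MSA against placebo

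*Combined protocol and SAP*

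**What the plan says.** All references are to the combined protocol and SAP.

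- **Hypothesis.** Research Hypotheses, item 1, predicts for the MSA group a "greater mean change from baseline to endpoint in total score as compared to the group treated with placebo". The Statistical Analysis section repeats this as an MSA-versus-placebo difference in MGH-CPFQ change. Neither place says which visit is the endpoint.
- **Timing.** The only timing statement is in the Study Design section: "The primary outcome measure will be the MGH-CPFQ total score at baseline and the MGH-CPFQ total score at the end of the trial".
- **Treatment by phase.** Study Design: "Study Phase 2 will consist of visits 6 through 8". Study Procedures: "Group 2: PBO during Phase 1 followed by MSA during phase 2". Group 1 takes MSA in both phases. Fig. 1 shows MSA in both columns at Visits 6 to 8.
- **Switch point.** Study Procedures: "Phase 2 study drug is dispensed at study visit 5". Visit 5 is therefore the last assessment at which Group 2 has had only placebo.
- **Model.** Study Design names a mixed-model repeated-measures analysis: "The independent variables will be the study visit, the treatment in the previous phase, and treatment assignment". It lists no visit-by-treatment term and no contrast.
- **Missing data.** Statistical Methods makes the last-observation-carried-forward (LOCF) data set primary. Study Procedures: "If a subject withdraws or is terminated early from the study, visit 9 procedures will be performed at the final study visit". Fig. 3 lists no MGH-CPFQ at Visit 9.
- **A second primary analysis.** Statistical Methods also describes the primary analysis as a CMH test on pooled MGH-CPFQ response rates. It names no visit or phase and does not define response.

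**The concern.** A randomized comparison with placebo has to be read while one group is still on placebo. Here that holds at Visits 3 to 5 only. Read at the end of the trial, the comparison is early start versus delayed start of the same drug. If Group 2 improves after switching, an effective drug can show little or no difference.

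A difference that does appear at Visit 8 is also hard to interpret. A Group 2 subject who leaves in Phase 1 after at least one post-baseline rating has no MGH-CPFQ at the exit visit, so a placebo-period score is carried into Visit 8. The Group 2 value then mixes MSA and placebo scores in proportions set by dropout. Neither kind of Visit 8 result answers the stated hypothesis, although data that could answer it are already being collected.

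**Working it through.** **1. What the end-of-trial score can be.** Fig. 3 marks MGH-CPFQ at Visits 1 to 8 and not at Visit 9, so the last available score is at Visit 8 (day 42).

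| Visit | Day | Group 1 | Group 2 | Difference between groups |
|---|---|---|---|---|
| 3, 4, 5 | 7, 14, 21 | MSA | placebo | MSA vs placebo |
| 6, 7, 8 | 28, 35, 42 | MSA | MSA | early vs delayed start |

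Nominal MSA exposure at Visit 8 is 42 days in Group 1 and 42 − 21 = 21 days in Group 2. The plan says "There is a one-week interval between study visits", with a window of ±3 days. If the window applies to each of the three Phase 2 intervals, Group 2 exposure runs from 3 × 4 = 12 to 3 × 10 = 30 days. If it applies to the scheduled days of Visits 5 and 8, the range is 21 ± 6, or 15 to 27 days. On either reading Group 2 has been on MSA for at least 12 days.

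**2. What a Visit 8 reading could cost.** The plan gives no alpha, effect size, SD or power, so its sample size cannot be reproduced and the following is illustration only. Inputs from the plan: 20 randomized per arm, with a floor of 12 evaluable per arm. Assumptions: two-sided alpha 0.05, a two-sample t-test in place of the planned methods, a standardized Visit 5 difference d, and a share r of it remaining at Visit 8.

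Power = P(|T| > t₀.₉₇₅), where T is noncentral t with 2n − 2 degrees of freedom and noncentrality r·d·√(n/2).

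| n per arm | Contrast | d = 0.5 | d = 0.7 | d = 0.9 |
|---|---|---|---|---|
| 20 | Visit 5 (r = 1) | 34% | 58% | 79% |
| 20 | Visit 8, half remains (r = 0.5) | 12% | 19% | 28% |
| 20 | Visit 8, full catch-up (r = 0) | 5% | 5% | 5% |
| 12 | Visit 5 (r = 1) | 22% | 38% | 56% |
| 12 | Visit 8, half remains (r = 0.5) | 9% | 13% | 18% |

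For 80% power at Visit 5, d must be about 0.91 with 20 per arm (noncentrality 0.909 × √10 = 2.87) and about 1.20 with 12 per arm. Visit 5 is not well powered either.

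**3. Whether the listed model terms settle the matter.** The three terms (visit, treatment, previous-phase treatment) were fitted by generalized least squares to expected values. Previous-phase treatment was coded as none in Phase 1 and as MSA or placebo in Phase 2. The true difference was 0 at Visits 6 to 8 throughout.

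| Visits fitted | Difference at Visits 3, 4, 5 | Treatment coded as | Treatment coefficient |
|---|---|---|---|
| 3–8 | d, d, d | group or current drug | 1.0d |
| 3–8 | d/3, 2d/3, d | group or current drug | 0.67d (independent, compound-symmetric); 0.70d (AR(1), ρ = 0.7) |
| 2–8 | d, d, d | group | 0.75d (independent, compound-symmetric); 0.65d (AR(1), ρ = 0.7) |
| 2–8 | d, d, d | current drug | 1.0d |

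In the first row with group coding, the previous-phase coefficient is −1.0d, so the fitted Visit 8 difference is 1.0d − 1.0d = 0. The same paragraph of the plan thus supports a treatment effect of d (the model coefficient) and of 0 (the end-of-trial outcome). When the effect builds over Phase 1, the coefficient averages over visits and does not isolate Visit 5.

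**4. LOCF.** Its effect on the Visit 8 difference is not quantified, because the documents give no dropout rate.

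**The case against.** The best defence is that the plan never literally commits to Visit 8. It names no visit for the end of the trial, it states an MSA-versus-placebo hypothesis that only Phase 1 can serve, and its model has a previous-phase term that makes sense only if the analysis distinguishes the phases. On that reading the time point is undefined rather than wrong, and the listed terms can recover a Phase 1 effect.

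The last point is true, and the table above shows it. But recovering that effect depends on which visits enter and how treatment is coded, and the plan specifies neither. The only timing sentence points to the end of the trial, where the schedule leaves no MGH-CPFQ visit other than Visit 8. The pooled response-rate analysis does not help, since it names no phase and competes with the mixed model.

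Four narrower objections stand in part:

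- At the floor of 12 evaluable per arm, Visit 5 power is clearly lower than at 20 per arm. Both sets of figures are shown.
- The model coefficient is 1.0d only under some codings. This adds to the ambiguity.
- Group 1 leavers also carry early scores forward, so LOCF does not affect Group 2 alone.
- A prespecified contrast averaged over Visits 3 to 5 would also be a valid randomized test. Visit 5 is one acceptable choice; a Phase 1 contrast is what is required.

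**Conclusion.** The concern holds and must be fixed. The primary outcome as written is read when neither group is on placebo, so it cannot test the primary hypothesis, and no section ties the endpoint to Visit 5 or Phase 1. This follows from the text and the schedule alone; it depends on no assumed number.

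The size of the loss does rest on assumptions. With 20 per arm and a true Visit 5 difference of 0.5 to 0.9 SD, power falls from 34–79% at Visit 5 to 12–28% at Visit 8 if half the difference persists, and to the 5% false-positive rate if Group 2 fully catches up.

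**What to change.** - In Research Hypotheses, Study Design and Statistical Analysis, define the primary endpoint as change in MGH-CPFQ total score from Visit 2 to Visit 5 (Week 3, end of Phase 1).
- Add a visit-by-treatment term to the mixed model and name the Group 1 minus Group 2 contrast at Visit 5 as the primary estimate.
- If LOCF is kept, carry forward only within Phase 1.
- Reconcile the pooled response-rate CMH analysis with this, so that there is a single primary analysis.
- Use Visit 5 for the placebo-compared secondaries collected there, such as MADRS, QIDS and CGI-I.
- Report Visits 6 to 8 as continuation versus delayed start, with no MSA-versus-placebo claim. The same applies to the HDRS, whose only post-baseline assessment is at Visit 8.

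**Cost.** These are text changes; MGH-CPFQ, MADRS, QIDS and CGI-I are already scheduled at Visit 5, so no visit or assessment is added. The efficacy claim is limited to three weeks, which is all the placebo control the design contains. The HDRS hypotheses lose their placebo comparison unless an HDRS rating is added at Visit 5, but the Visit 8 rating never provided that comparison.
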